### 9.3.1. Sites

For SAE Forms completed by someone other than the Investigator, the Investigator will be required to countersign the original SAE Form to confirm agreement with the causality and severity assessments. The form should then be returned to NCTU and a copy kept in the Site File. Investigators should also report SAEs to their own Trust where required by local practice.

### 9.3.2. NCTU

On receipt of an SAE form, seriousness and causality will be reviewed independently by the medical monitor (Chief Investigator or Deputy Medical Expert) responsible for determining causality assessments. An SAE judged by the Investigator or medical monitor (Chief Investigator or Deputy Medical Expert) to have a reasonable\* causal relationship with the trial medication will be regarded as a Serious Adverse Reaction (SAR). The Chief Investigator or Deputy Medical Expert will also assess all SARs for expectedness. If the event meets the definition of a SAR that is unexpected (i.e. is not defined in the current approved version of the Reference Safety Information (RSI)) it will be classified as a SUSAR (section 6.4.2). The Chief Investigator or Deputy Medical Expert will not downgrade an assessment of seriousness or causality made by the site PI, any changes to this assessment can only be an upgrade (unless the wrong category was selected in error when initially reported).

\*reasonable equates to possible, probable or definitely related in the opinion of either the Investigator or Chief Investigator

### 9.3.3. Provision of follow-up information

Participants should be followed up until resolution or stabilisation of the event. Follow-up information should ideally be provided on a new SAE Form.

## 9.4. Reporting period

Details of all ARs will be documented and reported from the date of commencement of protocol defined treatment until 7 days after the scheduled last treatment (day 90 pill to be taken). SAEs that are judged to be at least possibly related to the IMP must still be reported in an expedited manner irrespective of how long after IMP administration the reaction occurred.

## 9.5. Reporting to the Competent Authority and Research Ethics Committee

### 9.5.1. Suspected Unexpected Serious Adverse Reactions

The NCTU will report a minimal data set of all individual events categorised as a fatal or life threatening SUSAR to the Medicines and Healthcare products Regulatory Agency (MHRA) and Research Ethics Committee (REC) within 7 days. Detailed follow-up information will be provided within an additional 8 days.

All other events categorised as SUSARs will be reported within 15 days.

### 9.5.2. Serious Adverse Reactions

The NCTU will report details of all SAEs and SARs (including SUSARs) to the MHRA and REC annually from the date of the Clinical Trial Authorisation, in the form of a Development Safety Update Report (DSUR).

### 9.5.3. Adverse Reactions

Details of all ARs will be reported to the MHRA on request.

### 9.5.4. Other safety issues identified during the trial

The MHRA and REC will be notified immediately if a significant safety issue is identified during the trial.

### 9.6. Reporting to Investigators

Details of all SUSARs and any other safety issue which arises during the trial will be reported to Principal Investigators. A copy of any such correspondence should be filed in the Investigator Site File.

### 9.7. Reporting to Data Monitoring Committee

The independent DMC will review all SAEs.

### 9.8. Reporting to third parties

No reporting of adverse events to third parties is expected. Any safety issues identified during the trial will be notified to the MHRA.

## 10. Study Within A Trial (SWAT)

### 10.1. Background

Trial participant information sheets are often only provided in written English, which may limit trial participation for people who have difficulty understanding written English. It is important to make participation in clinical trials as inclusive as possible and researchers are exploring the best ways to do this. Media tools are increasingly used to engage potential participants, but there is limited data on how to best do this. Testimonies from previous participants show that media tools probably increase recruitment, as they provide potential participants with evidence that people like them engage with research [22]. No comparable data exists for use of video clips, which are ubiquitous on social media.

Our SWAT will investigate whether watching a patient testimony video clip, available in English, Polish, Romanian and Punjabi in addition to reading the written participant information sheet increases consent rates compared to written information alone.

### 10.2. Interventions

Group 1: Written participant information only

Group 2: Written participant information followed by patient video testimony

### 10.3. Method of allocation

Randomisation for the SWAT will occur at site level (cluster) to prevent contamination with the intervention. Sites will be randomised in 1:1 ratio to either use the video clip for recruitment or not using stratified block randomisation. Randomisation will be stratified by the size of the site (large vs small). An independent study statistician will generate the randomisation schedule. For sites randomised to use of the video clip, a link to the video clip will be given on the PIS and a QR code for the video clip that participants can scan using their phones, will be on the PIS. Participants would need to have the opportunity to watch the video clip prior to being randomised in the main trial.

#### 10.4. Outcome measures

The primary outcome will be the proportion of eligible patients who consent to the trial.

The secondary outcome will be the proportion of randomised participants who provide primary outcome.

#### 10.5. Sample size

The sample size for the SWAT will be predicated by that of the DEBI trial. We anticipate including at least 17 sites in the SWAT. More detailed information on the sample size will be detailed in the SWAT statistical analysis plan.

#### 10.6. Analysis

Detailed analysis of this SWAT will be documented in the trial SWAT statistical analysis plan. Analysis will be based on cluster-level summaries. Unpaired t-test, with each cluster weighed by its sample size, will be used to provide 95% confidence intervals for the between-group effect measures.

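### The SWAT stratifies sites by size but its named t-test has no stratum term, so its interval will be wider than necessary if consent or retention differs by site size

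*Protocol*

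**What the plan says.** The SWAT compares written information alone with written information plus a patient video, and allocates whole sites: "Randomisation for the SWAT will occur at site level (cluster) to prevent contamination with the intervention". On the method, section 10.3 says "Sites will be randomised in 1:1 ratio to either use the video clip for recruitment or not using stratified block randomisation", and names one stratification factor: "Randomisation will be stratified by the size of the site (large vs small").

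Section 10.4 sets the primary outcome: "The primary outcome will be the proportion of eligible patients who consent to the trial". The secondary outcome is the proportion of randomised participants who provide the main trial's primary outcome. Section 10.5 gives the number of clusters ("We anticipate including at least 17 sites in the SWAT") and leaves further sample size detail to a SWAT statistical analysis plan.

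Section 10.6 opens with a deferral ("Detailed analysis of this SWAT will be documented in the trial SWAT statistical analysis plan"), then fixes the level of analysis ("Analysis will be based on cluster-level summaries") and the method: "Unpaired t-test, with each cluster weighed by its sample size, will be used to provide 95% confidence intervals for the between-group effect measures". It mentions no stratum, covariate or other adjustment.

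**The concern.** Stratified allocation puts nearly equal numbers of large and small sites in each arm, so a difference between large and small sites contributes little to the arm comparison. A two-group t-test does not use this. It measures scatter around each arm mean, and that scatter still contains the large-small difference. If site size predicts the outcome, the standard error is larger than the design warrants. Weighting clusters by sample size does not help, because weights do not remove a difference in mean between strata.

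With about 17 clusters, precision is scarce. Section 10.7 offers the results to people conducting meta-analyses, so an avoidably wide interval would carry forward. Site size is the only stratification factor, which suggests that the designers thought it could matter.

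**Working it through.** **Inputs from the protocol.** Sites are the clusters, allocated 1:1 in two size strata (10.3). There are at least 17 sites (10.5). The test is an unpaired t-test on cluster summaries, weighted by cluster size (10.6).

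**Inputs not in the protocol.** It gives no SWAT effect size, power, consent rate, between-site SD, cluster sizes or split of sites by size. There is therefore no SWAT figure to reproduce, and what follows rests on assumed values.

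**Step 1: price of a stratum term.** With 17 sites, the two-group test has 17 − 2 = 15 degrees of freedom and the stratum-adjusted analysis has 17 − 3 = 14. The 97.5% t quantiles are 2.131 and 2.145, and their ratio is 1.006. If nothing else changes, adjusting widens the interval by 0.6%.

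**Step 2: closed form, equal weights and equal strata.** Let D be the large-minus-small difference and s the within-stratum SD of the site summaries. Stratum means lie D/2 from the overall mean, which adds 17 × (D/2)² to the error sum of squares, spread over 15 degrees of freedom. The ratio of unadjusted to adjusted half-width is

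R = √(s² + (D/2)² × 17/15) × t15 / (s × t14).

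With s = 0.10 and D = 0.10: √(0.01 + 0.0025 × 1.133) = 0.1133, and 0.1133/0.10 × 2.131/2.145 = 1.13. With D = 0.20: √(0.01 + 0.01 × 1.133) = 0.1461, giving 1.45.

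**Step 3: simulation of the size-weighted test.** Assumptions: 8 large and 9 small sites, about 100 and 30 eligible people per site, mean consent 55%, between-site SD 0.10 within strata plus binomial variation, and a true effect of 15 points. There were 6,000 repeats per setting (4,000 for type I error). The same weights were used with and without a stratum term. Paired entries are unadjusted / adjusted.

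| Gap D | R, closed form | R, simulated | Power | Coverage | Type I error |
|---|---|---|---|---|---|
| 0 | 0.99 | 0.99 | 69% / 68% | 91.8% / 91.9% | 8.7% / 8.4% |
| 5 points | 1.03 | 1.01 | 69% / 69% | 92.5% / 92.0% | 8.4% / 8.6% |
| 10 points | 1.13 | 1.07 | 64% / 68% | 93.3% / 91.5% | 6.4% / 8.0% |
| 20 points | 1.45 | 1.28 | 51% / 69% | 97.3% / 92.6% | 3.1% / 7.4% |

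Two features pull the simulated ratios below the closed form. Binomial variation adds to the within-stratum scatter. Large sites also carry about 800/(800 + 270) = 75% of the weight, so the weighted between-stratum variance is about 0.75 × 0.25 × D² = 0.19D², against 0.25D² for equal strata.

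**Step 4: reading the table.** Adjusted coverage stays near 92% at every gap, so the shortfall from 95% does not come from the missing stratum term. It comes from the weights. At 55% consent the variance of a site proportion is 0.01 + 0.2475/100 = 0.0125 for a large site and 0.01 + 0.2475/30 = 0.0183 for a small one, a ratio of about 1.5, while the weights imply 100/30 = 3.3. The power figures therefore compare tests with unequal type I error, both above 5% at gaps of 0 to 10 points. They show the direction and rough size of the loss rather than calibrated power.

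**The case against.** **The detail is deferred to a SWAT analysis plan that is not shown.** Adjustment is often left to such a plan, and section 10.6 does not forbid it. That would be decisive had 10.6 left the method open. It does not: it names the test that will produce the intervals. A SWAT plan that follows the protocol inherits the unadjusted test, and one that adds a stratum term departs from it.

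**No document shows that size matters.** This stands, and it limits the claim. A reader might infer that the interval is certainly too wide and power certainly lost. The protocol does not support that: it gives no rates by site size, and at gaps of 0 to 5 points the loss is about nil or slightly reversed. Nor is the planned interval too wide in absolute terms at small gaps, since its simulated coverage was below 95% because of the weights. The case is weaker still for the secondary outcome, because section 8.2.7 has the trials unit coordinate most follow-up without further site involvement.

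**Larger losses can be calculated.** An unweighted test with 18 sites of 60 people, a between-site SD of 8 points and a 20-point gap gives power of 53% against 82%. That is not the planned weighted test, and the gap would make size account for 10²/(10² + 8²) = 61% of the true between-site variance. Nothing in the protocol supports so strong a relation.

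**The omission is conservative.** Also true. Leaving out the stratum neither biases the estimate nor inflates type I error.

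**Conclusion.** The protocol stratifies SWAT allocation by site size and then fixes an analysis that does not use the stratification. The interval will be wider than necessary, and power lost, if consent or retention differs between large and small sites.

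With 17 sites and a within-stratum SD of 10 points, both assumed in part or whole, the loss is about nil for a gap of 0 to 5 points. It is 7 to 13% of interval width for 10 points and 28 to 45% for 20 points, with simulated power about 4 and 18 percentage points lower. The ranges span the closed form and the size-weighted simulation.

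It would be too much to say that the unadjusted test brings no gain, since it keeps one degree of freedom. A reader should also not infer any effect on the non-inferiority comparison, which this analysis does not enter. This is a minor precision improvement, confined to the SWAT. It is worth making because the possible gain far exceeds the price.

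**What to change.** In section 10.6, replace the two-group t-test with a cluster-level linear regression of the site proportion on video arm and the size stratum used at randomisation. Take t-based 95% confidence intervals on (number of sites − 3) degrees of freedom, for both SWAT outcomes. If the unadjusted test is kept, state why. Carry the same wording into the SWAT analysis plan.

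The choice of cluster weights is a separate matter and this change does not settle it. If weighting by sample size is retained, the same weights can be used in the regression, but the stratum term will not correct the under-coverage that those weights produced in the simulation.

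The cost is one sentence and one degree of freedom, with no new data.

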#### 10.7. Dissemination

The SWAT will be registered on the Northern Ireland MRC Trials Hub for Methodology Research SWAT registry. The findings will be made publicly available as soon as possible after the end of the SWAT and will be made available to researchers conducting meta-analysis in this field.

### 11. Data Handling and Record Keeping

#### 11.1. Source Data

To allow for the accurate reconstruction of the trial and clinical management of the participant, source data will be accessible and maintained.

Source data is kept as part of the participant's medical notes generated and maintained at site. Each site will record the location of source data at their site using a source data location log prior to commencing recruitment. Data that are not routinely collected elsewhere may be entered directly onto the CRF; in such instances the CRF will act as source data and this will be clearly defined in the source data location log and recorded.

For this trial, source data refers to, though is not limited to, the participant's medical notes, laboratory results for tests recorded as part of the baseline visit data collection, data recorded directly into the CRF, and patient reported follow-up data (bleeding diary, adherence and follow-up questionnaires).

All data collected directly from participants will be considered as source data within the CRF. Where paper questionnaires are issued to participants these will be returned to the NCTU for data entry and will be considered source data. Where questionnaire data is obtained via telephone, this data will be entered directly into the CRF by a member of the NCTU and will be considered source data.

#### 11.2. CRF Completion

Data for the trial will be captured directly into a REDCap CRF. Data reported on each CRF will be consistent with the source data and any discrepancies will be explained. Staff delegated to complete CRFs will be GCP trained and receive trial-specific training from the NCTU team on how to complete

these correctly.

In all cases it remains the responsibility of the site's Principal Investigator to ensure that the CRF has been completed correctly and that the data are accurate. Where applicable for the trial this will be evidenced by the signature of the site's Principal Investigator on the CRF. It is the responsibility of the Principal Investigator to ensure there are site staff in place locally to complete data entry into the eCRF in a timely manner.

Site staff are only required to complete the CRF for the baseline visit and standard follow up review at 90 days. This must be done within 7 days of the visit date.

Bleeding diary, treatment adherence and participant questionnaire data will be captured directly into the eCRF where possible using the MyCap application or other electronic responses (e.g. email containing link to questionnaire). Where information is completed by the participant on paper, the completed originals will be sent to the Trials Office to be entered by a member of the NCTU.

### 11.3. Data Management

All trial data will be entered into REDCap with each participant assigned an enrolment and randomisation number for use on CRFs and other trial documents. The documents and database will also use their initials (of first and last names separated by a hyphen or a middle name initial when available) and date of birth.

Participant contact details will be logged separately to the trial CRF data, to ensure participant identifiable data is separate to data used for analysis. Participant contact details may also be used by the trial team to send out trial related questionnaires and correspondence limited to the duration of the participant's participation in the trial or to share the trial results once the trial has been published.

The database will have in-built validation to ensure that the identifiers used all match with the allocated participant ID number. CRFs will be treated as confidential documents and held securely in accordance with regulations. Access to REDCap will be restricted and secure and CRFs will be restricted to those personnel approved by the CI or local PI and recorded on the trial delegation log. Missing or ambiguous data will be queried with the site via the CRF and sites should respond to the data queries in a timely manner, ideally within 2 weeks of the query being raised. Errors will be corrected and recorded on the CRFs on the audit log. The CI or local PI (or their designee) will sign a declaration ensuring accuracy of data recorded in the CRF.

The CRF will only collect the minimum required information for the purposes of the trial. Access to the information will be limited to the trial staff, investigators, authorised sponsor representatives and relevant regulatory authorities (see above). Electronic data including the trial database will be held securely and password protected restricted to those approved requiring access for the trial.

For the electronic daily bleed and treatment adherence diary, a MyCap push notification will be sent to each participant. For questionnaire data collected electronically (30-, 60- and 90-day questionnaires), a secure link to an online questionnaire will be sent. Where paper copies of diaries or questionnaires are used, a paper version of the questionnaire will be sent by NCTU to the contact address provided by the participant at their baseline visit, with a pre-paid return envelope.

Questionnaires returned to NCTU will be entered by a member of NCTU and a sample will be reviewed by a separate member of the NCTU. Further details will be documented in the current version of the DMP. Data obtained from participant reported outcomes will not be subject to data queries. Decisions on how to treat anomalous data will be made by members of the TMG blinded to allocations and documented in the current version of the DMP and/or Statistical Analysis Plan.

#### 11.4. Archiving

It is the responsibility of the PI to ensure all essential trial documentation and source documents (e.g. signed ICFs, Investigator Site Files, Pharmacy Files, participants' medical records, copies of CRFs etc.) at their site are securely retained for at least 7 years to comply with The Medicines for Human Use (Clinical Trials) Regulations 2004 and Sponsor requirements.

In compliance with the ICH/GCP guidelines, regulations and in accordance with the University of Nottingham Code of Research Conduct and Research Ethics, the Chief or local Principal Investigator will maintain all records and documents regarding the conduct of the trial. These will be retained for at least 7 years or for longer if required. If the responsible investigator is no longer able to maintain the trial records, a second person will be nominated to take over this responsibility.

The Trial Master File and trial documents held by the CI on behalf of the Sponsor shall be finally archived securely in the Microsoft cloud which has multiple redundant systems and backup services. This archive shall include all trial databases and associated meta-data encryption codes. Access to files once archived (e.g. for inspection purposes), will be managed by the NCTU archivist and will only be accepted on approval of the University of Nottingham sponsor

#### 11.5. Data Sharing

Individual participant medical information obtained as a result of this trial is considered confidential and disclosure to third parties is prohibited with the exceptions noted in this protocol.

Participants' contact details, including name, address, telephone/mobile number and email will be shared between participating sites, NCTU and third parties (where required) for the purposes of contacting participants relating to their participation in the trial (e.g. questionnaire reminders, data collect etc).

Any personal data will be held in a secure database using encryption, with restricted password protected access. Only appropriate members of the participating site team and NCTU research team will have access to these data.

Participant confidentiality will be further ensured by utilising identification code numbers to correspond to treatment data in computer files.

Data generated as a result of this trial will be available for inspection on request by the University of Nottingham, NCTU, the REC, local Research and Development departments and the regulatory authorities.

Anonymised participant data may be shared with researchers external to the trial research team in accordance with the NCTU's data sharing procedure and the National Institute for Health Care Research (NIHR) policy on the sharing of research data. All requests for data should be sent to the Nottingham Clinical Trials Unit.

## 12. Quality control and quality assurance

### 12.1. Site Set-up and Initiation

All participating PIs will be asked to sign the necessary agreements and supply a current CV to NCTU – this should be signed within the last 2 years. All members of the site research team will also be required to sign a site delegation and training log. Prior to commencing recruitment all sites will undergo a process of initiation and will have completed any necessary training. Key members of the site research team will be required to watch a training session or attend either a meeting (virtual or in-person) covering aspects of the trial design, protocol procedures, adverse event reporting, collection and reporting of data and record keeping. Sites will be provided with an Investigator Site File containing essential documents, instructions, and other documentation required for the conduct and reconstruction of the trial. NCTU must be informed immediately of any change in the site research team.

